8.7. Extent of Exposure

Exposure data will be listed but not summarized.

8.8. Treatment Compliance

Not Applicable.

This document is confidential.

9. Pharmacokinetics

Pharmacokinetic analyses will be performed using the PKDS-CO and PKDS-E.

PK parameters will be calculated for total and PUF molybdenum (as surrogate measures of ALXN1840 PK) using noncompartmental methods with Phoenix® WinNonlin® (Certara USA Inc., Princeton, New Jersey) Version 8.0 or higher. Calculations of individual PK parameters will be based on measured total molybdenum and, when feasible, PUF molybdenum concentrations and the actual sampling times elapsed from the actual reference dosing time data recorded during the study.

9.1. PK Sampling Schedule

Two-way cross-over treatment periods

Blood samples for PK analysis of total and PUF Mo (as surrogate measures of ALXN1840 PK) and pharmacodynamic (PD)/biomarkers will be collected in each dosing period on Day 1 at pre-dose, and postdose at 1, 2, 3, 4, 5, 6, 8, 12 and 24 hours (Day 2) and then at 24 hour intervals on Days 3, 4, 5, 6, 7, 8, 9, 10, and 11.

The 336-hour sample for Dosing Period 1 will be collected predose in Dosing Period 2. Participants may be discharged on Day 11 of each dosing period after completion of all procedures and review of all safety data. The end of Dosing Period 2 will occur on Day 15 ± 2 of Dosing Period 2, with the collection of the 336-hour PK sample for Dosing Period 2.

Dose-proportionality extension period

The Dose-Proportionality Extension Period will be conducted following completion of the Two-way Crossover Periods of the study and after an at least 14-day washout period.

A similar schedule for PK samples collection will be followed in the dose proportionality extension period as two-way cross-over treatment periods. Further details are given in [Section 4.6](#).

9.2. Plasma PK Endpoint

Following PK parameters will be derived from the plasma concentrations of total and PUF molybdenum when feasible and supported by the available data.

- Time delay between the time of dosing and time of appearance of drug concentration in plasma (Tlag; for plasma total molybdenum with ALXN1840 administration)
- Maximum observed concentration in plasma (C_{max})
- Molybdenum dose-normalized C_{max} (C_{max_n}); n = dose normalized
- Time to C_{max} (T_{max})
- Area under the plasma concentration (AUC) versus time curve from time 0 to the last quantifiable concentration (AUC_t)
- Molybdenum dose-normalized AUC_t (AUC_{t_n})
- AUC versus time curve from time 0 to infinity (AUC_{∞})

This document is confidential.

- Molybdenum dose-normalized AUC_{∞} (AUC_{∞_n})
- AUC extrapolated from time t to infinity as a percentage of total AUC_{∞} ($\%AUC_{\text{extrap}}$)
- Apparent terminal-phase elimination rate constant (λ_z)
- Terminal elimination half-life ($t_{1/2}$)
- Apparent oral clearance (CL/F)
- Apparent volume of distribution (V_d/F)
- Relative bioavailability (F_{rel}) between test and reference treatments

Additional plasma PK parameters may be calculated if deemed appropriate.

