4.2. Scientific Rationale for Study Design

This study is being conducted in healthy participants so that the assessments are not confounded by disease activity, comorbidities, or concomitant medications. The inclusion and exclusion criteria for this study are consistent with Phase 1 clinical pharmacology studies that assess the medication of interest and to minimize assignment bias. As the key objectives of the study are assessments of bioavailability and dose-exposure proportionality, a blinded design is not necessary.

The Two-way Crossover Period was adopted to control the variability within and between participants. A minimum of 14 days between dose administration is considered sufficient to eliminate, on average, approximately more than 99.2% of the plasma total Mo.

Following ALXN1840 administration, the active drug moiety tetrathiomolybdate rapidly binds Cu to form the TPC in the liver and blood and presents as such in the systemic circulation. If TPC is not rapidly formed, tetrathiomolybdate spontaneously undergoes serial hydrolysis to form molybdate, the most common form of nutrient Mo, and is excreted in the urine. Total Mo concentration has been measured as a surrogate of ALXN1840 PK; however, total Mo concentration cannot distinguish whether the Mo is complexed with Cu and albumin (as in TPC), free active ALXN1840 drug, intermediate hydrolysis products, or molybdate which may be from ALXN1840 hydrolysis. To better characterize the amount of non-TPC bound ALXN1840 and its degradation products, PUF Mo, which represents the free parent drug (ALXN1840), short-lived intermediate hydrolysis products, and molybdate, will be measured. Total Mo and PUF Mo concentrations also include physiologic molybdate concentrations from dietary micronutrient molybdate intake. While it is not feasible to separate and quantify ALXN1840 directly in the

plasma, total Mo PK and PUF Mo PK provide surrogate measures to characterize ALXN1840 exposure. To better characterize the absorption, distribution, metabolism, and excretion (ADME) of ALXN1840, the PK of both total Mo and PUF Mo will be characterized and described. The primary PK measure is total Mo, whereas PUF Mo is an exploratory measure.

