For patients aged 3 to < 6 years, the population PK modeling results showed that a 5 mg dose has comparable exposure to 15 mg administered to adult patients, and that a 15 mg dose has a higher exposure than 30 mg, but a lower exposure than 60 mg administered to adult patients. Hence, the predicted dose range for patients aged 3 to < 6 years is 5 mg to 15 mg, which is anticipated to provide comparable safety and efficacy outcomes to those in adolescent and adult patients over 12 years of age with a dose range of 15 mg to 60 mg currently allowed in the ongoing Phase 3

Study WTX101-301. Therefore, the EC mini-tablet doses of 2.5, 5, 10, 15, and 30 mg will be tested in this study, which covers the entire anticipated dose range recommended in the planned study in the pediatric population.

An inductively coupled plasma-mass spectroscopy (ICP-MS) method, with a lower limit of quantification (LLOQ) of 1.00 ng/mL and 0.25 ng/mL for the assays of total Mo and PUF Mo, respectively, has been previously implemented for analyzing plasma samples from Study WTX101-HV-106. In that study, for the 15 mg and 60 mg doses, %AUC_{extrap} ranged from 1.3% - 12.2% (all were less than 20%). In the current study, a maximum observed concentration (C_{max}) for total Mo of approximately 40 ng/mL is anticipated after the lowest ALXN1840 dose of 2.5 mg and with an assay LLOQ of 1.00 ng/mL, it would be possible to detect measurable total Mo concentrations at a mean of 1.25 ng/mL for approximately 5 half-lives with reasonably low expectation for excess AUC extrapolation of over 20% for AUC_∞ estimation. A C_{max} for PUF Mo of approximately 2 ng/mL is anticipated after the lowest ALXN1840 dose of 2.5 mg and with an assay LLOQ of 0.25 ng/mL, it would be possible to detect measurable PUF Mo concentrations at a mean of 0.25 ng/mL for approximately 3 half-lives with possibility of AUC extrapolation of over 20% for AUC_∞ estimation.

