9.3. Presentation of Concentration Data

9.3.1. Handling of Missing Data

Missing concentration data for all participants who are administered scheduled study treatments will be considered as non-informative missing and will not be imputed. No concentration estimates will be provided for missing sample values.

For the derivation of AUC and for the individual plasma concentration versus time curves, the following rules will apply:

- Concentration values below the assay's lower limit of quantification (BLQ) in pre-dose Day 1 samples will be treated as zero;
- The sampling time of pre-dose samples relative to dosing will also be treated as zero;
- BLQ's between two quantifiable samples will be set to missing;
- The first BLQ after the last measurable sample will be set to missing; any subsequent BLQ's will be set to zero;

For plasma concentration summary the following rules will apply:

- All BLQ values will be set to zero;
- No further imputation will be applied to any missing values.

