9.4. Derivation of Pharmacokinetic Parameters

- The apparent C_{max} and the corresponding t_{max} along with T_{lag} will be read directly from the concentration-time plot (observed data).
- AUC_t will be calculated using the log-linear trapezoidal interpolation rule for extravascular model.
- The terminal elimination rate constant (λ_z) will be determined by log linear regression obtained on at least the 3 last quantifiable concentrations and will not include C_{max} ; $t_{1/2}$ is calculated by the program as $\ln 2/\lambda_z$;
- AUC_{∞} will be calculated by the program as: $AUC_{\infty} = AUC_t + AUC_{extrap}$ where last is the sampling time point of the last measurable concentration (t_{last}). AUC_{extrap} will be calculated by the program as: C_{last}/λ_z , where C_{last} is the observed concentration at time t_{last} and λ_z is the elimination rate constant during the apparent terminal elimination phase. AUC_{∞} will only be presented for participants with a reliable λ_z ;
- CL will be calculated by program as (molybdenum dose amount/ AUC_{∞});
- V_z will be calculated by the program as (molybdenum dose amount/ AUC_{∞})/ λ_z ;
- Dose normalized PK parameters will be calculated using the equivalent molybdenum dose and not the ALXN1840 dose. .

The following PK acceptance criteria will be applied to assess the reliability of elimination parameters:

- Number of points to calculate λ_z is greater than or equal to 3 excluding C_{max} point;
- The adjusted square of the correlation coefficient or coefficient of determination (Rsquare adjusted) for the goodness of fit of the regression line through the data points must be ≥ 0.90 ;
- $AUC_{extrap} \leq 20\%$.

Unreliable PK parameters will be listed but flagged and excluded from summary.

This document is confidential.

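### Tlag for total Mo ignores the pre-dose level, which on the protocol's figures would often be quantifiable before Period 2 and the Extension

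*SAP*

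**What the plan says.** SAP 9.2 (and protocol 9.4.3) lists Tlag for total Mo among the plasma PK parameters, as "Time delay between the time of dosing and time of appearance of drug concentration in plasma". SAP 9.4 states the derivation: Tlag, like Cmax and Tmax, "will be read directly from the concentration-time plot (observed data". Neither section gives a threshold, a baseline correction, or a rule for a pre-dose sample that is quantifiable. SAP 9.3.1 places the pre-dose sample at time zero and replaces its value by zero only if it is BLQ, so a quantifiable pre-dose value stays in the profile.

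The protocol gives reasons to expect such values:

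- Section 4.2, on washout: "A minimum of 14 days between dose administration is considered sufficient to eliminate, on average, approximately more than 99.2% of the plasma total Mo".
- Section 4.2, on background: "Total Mo and PUF Mo concentrations also include physiologic molybdate concentrations from dietary micronutrient molybdate intake".
- Section 4.3, on the assay: "lower limit of quantification (LLOQ) of 1.00 ng/mL and 0.25 ng/mL for the assays of total Mo and PUF Mo, respectively".
- Section 4.3, on exposure, a Cmax "for total Mo of approximately 40 ng/mL is anticipated after the lowest ALXN1840 dose of 2.5 mg".

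Tlag is summarized descriptively (SAP 9.4.1). SAP 7.1 lays out the crossover tables in columns for Treatments A and B and allows a split by period where appropriate. The ANOVA in SAP 9.5 covers Cmax, AUCt and AUC∞ only.

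**The concern.** The definition presupposes a profile that starts from nothing. Total Mo does not start from nothing if a 15 mg dose was given 14 days earlier and diet contributes as well. If the time-zero value is already quantifiable, concentration has appeared at time 0 on the plain words of the definition, and Tlag is 0 whatever the enteric coating does.

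In a balanced AB/BA design, half of each treatment's Tlag values come from Period 2, so zeros there pull both treatment means down and shrink the difference between them. Both products are enteric-coated, so delay to onset is a natural descriptive comparison between twelve small units and one tablet. The interim analysis in SAP 13 takes in all PK data, which would include this summary. In the Extension every profile follows a 15 mg dose, so the lag at each mini-tablet dose would be understated.

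**Working it through.** **Inputs.** Anticipated Cmax 40 ng/mL at 2.5 mg and LLOQ 1.00 ng/mL (protocol 4.3). Minimum washout 14 days = 336 h, with elimination of about 99.2% or more on average (protocol 4.2). A 15 mg dose precedes both Period 2 and the Extension (protocol 1.2). Allocation is 24 AB and 24 BA (SAP 4.3).

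**1. Reproduce the protocol's figures.** With mono-exponential decline, 1 − 2^−7 = 99.22%, so 14 days is 7 half-lives and the implied half-life is 336/7 = 48 h. The same convention gives the 1.25 ng/mL at 5 half-lives in protocol 4.3: 40/2^5 = 1.25.

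**2. Expected pre-dose level from drug alone.** Assume dose-linear Cmax.

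- Peak at 15 mg: 40 × 15/2.5 = 240 ng/mL.
- Before Period 2: 240 × 2^−7 = 1.88 ng/mL (240 × 0.008 = 1.92 at exactly 99.2%).
- Before the Extension, after two doses: 240 × (2^−7 + 2^−14) = 1.89 ng/mL.

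All are above 1.00 ng/mL. Reaching the LLOQ from 240 ng/mL takes log2(240) = 7.91 half-lives, or about 380 h at 48 h each.

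**3. What would bring the average below the LLOQ.**

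- Elimination above 1 − 1/240 = 99.58%, meaning a half-life below 336/7.91 = 42.5 h. At 40 h the residual is 0.71 ng/mL.
- Or Cmax rising with dose to a power b with 40 × 6^b × 2^−7 < 1, meaning b < ln(3.2)/ln(6) = 0.65. At b = 0.8 the residual is still 1.31 ng/mL.

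**4. Share of profiles affected.** Take half-life as log-normal with median 48 h and an assumed between-participant CV, with σ = √ln(1 + CV²). The share with a quantifiable pre-dose value from drug alone is p = 1 − Φ(ln(42.5/48)/σ). If Tlag is 0 in a share p of Period 2 profiles and Period 1 is clean, each treatment mean becomes (1 − p/2) times its true value, and so does the A-B difference.

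| Assumed CV | p, drug alone | Difference retained, 1 − p/2 | p with assumed 0.5 ng/mL dietary Mo | Difference retained |
|---|---|---|---|---|
| 10% | 0.89 | 0.56 | 0.99 | 0.50 |
| 20% | 0.73 | 0.63 | 0.89 | 0.56 |
| 30% | 0.66 | 0.67 | 0.79 | 0.60 |
| 40% | 0.62 | 0.69 | 0.73 | 0.63 |

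In the limit p = 1, a true 1 h difference reads as 0.5 h. If the median half-life were 42.5 h, p would be 0.5 and 0.75 would be retained. The documents give no dietary Mo level. If it alone reached 1.00 ng/mL, Period 1 Tlag would be zero too and the whole difference would be lost.

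**5. Extension.** Every profile follows a 15 mg dose, so mean Tlag is about (1 − p) of its true value: 0.11 to 0.38 for p from 0.89 to 0.62.

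**The case against.** **Reading from a plot leaves room for judgement.** A pharmacokineticist who sees a curve sit near 1.9 ng/mL and then climb could take the climb as the appearance of drug. That stands. A reader might infer that Tlag is zero by construction in Period 2 and the Extension. The documents do not fix that outcome: zero is the literal reading, and the result is otherwise left open. Two analysts could then derive different values from the same data.

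**The inputs lean one way.** The documents give no 15 mg Cmax, and dose linearity is what the secondary objective examines. The 99.2% is an approximate lower bound over a minimum washout, so 48 h is about the longest average half-life that the sentence allows. A 16-day interval would leave 240 × 2^−8 = 0.94 ng/mL. This stands as a limit on size. Against it, the stated duration of about 10 weeks matches 28 days of screening plus three 14-day intervals (70 days), and dietary Mo pushes the other way.

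**Halving is a limiting case.** A reader might infer that the formulation difference is simply halved. That needs every Period 2 profile to read zero. The Extension gives mini-tablets only, so it has no bearing on the A-B difference.

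**The BLQ rule adds almost nothing.** A reader might infer from SAP 9.3.1 ("BLQ's between two quantifiable samples will be set to missing") that early BLQ samples after a quantifiable pre-dose value are erased, and the lag with them. At a 48 h half-life the residual falls only by a factor of 2^(2/48) = 1.029 in 2 h. Assay noise aside, the pre-dose value would have to lie between 1.00 and about 1.03 ng/mL. At 1.88 ng/mL the 2 h value is still about 1.82.

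**Tlag is a small part of the analysis and is recoverable.** It is not among the primary, secondary or exploratory endpoints. Concentrations and actual times are listed, so it can be re-derived. Sampling is hourly to 6 h, so a shift of 0.5 h in the mean is less than one sampling interval. All of this stands and bounds the importance of the point.

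**Conclusion.** The point holds as a defect in a descriptive parameter. The Tlag definition has no reference to the pre-dose level. On the protocol's figures, mean pre-dose total Mo before Period 2 and the Extension is about 1.9 times the LLOQ before any dietary Mo is added. Followed literally, the definition gives zero in roughly 62% to 89% of those profiles, keeps about 0.5-0.7 of the true A-B difference, and understates lag at each Extension dose.

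These sizes rest on dose-linear Cmax, mono-exponential decline, a 48 h median half-life, assumed CVs of 10% to 40%, and Period 1 profiles that start below the LLOQ. Faster elimination makes the effect smaller, and dietary Mo makes it larger. Tlag does not enter the ANOVA for relative bioavailability or the power model, so no primary or secondary conclusion depends on it.

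**What to change.** In SAP 9.2 and 9.4, define Tlag as the last sampling time before total Mo first exceeds that period's own pre-dose value by a pre-specified margin, for example one LLOQ (1.00 ng/mL). In SAP 9.4.1, summarize Tlag by treatment and period, so that any remaining effect of carry-over can be seen.

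Where the pre-dose sample is BLQ it already counts as zero under SAP 9.3.1, so the rule then amounts to the first value above the LLOQ. Using the pre-dose value as the reference is reasonable because the residual falls only about 3% in 2 h at a 48 h half-life. The margin is somewhat arbitrary, though one LLOQ is only 1/40 = 2.5% of the peak anticipated at the lowest dose. The cost is a few lines in the SAP and one derived variable, with no new samples. It should be settled before the interim analysis is run.

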9.3. Presentation of Concentration Data

9.3.1. Handling of Missing Data

Missing concentration data for all participants who are administered scheduled study treatments will be considered as non-informative missing and will not be imputed. No concentration estimates will be provided for missing sample values.

For the derivation of AUC and for the individual plasma concentration versus time curves, the following rules will apply:

- Concentration values below the assay's lower limit of quantification (BLQ) in pre-dose Day 1 samples will be treated as zero;
- The sampling time of pre-dose samples relative to dosing will also be treated as zero;
- BLQ's between two quantifiable samples will be set to missing;
- The first BLQ after the last measurable sample will be set to missing; any subsequent BLQ's will be set to zero;

For plasma concentration summary the following rules will apply:

- All BLQ values will be set to zero;
- No further imputation will be applied to any missing values.

9.3.2. Listing and Presentation of Individual PK Data

The actual and nominal sampling times of PK blood sample collection will be listed for each participant and will include the deviation in time from the protocol scheduled time (i.e., nominal time), if applicable.

All measured concentrations will be presented in original precisions (i.e., significant figures) and units as reported by Bioanalytical lab – eg ng/mL.

This document is confidential.

Plasma concentrations of total and PUF molybdenum and time deviation data will be presented in a data listing by participant.

9.3.3. Summary of PK Concentrations by Matrix

Plasma concentration data will be summarized separately by time point for each treatment using the following descriptive statistics: number of participants, arithmetic mean, SD, CV, geometric mean, geometric CV, median, minimum, and maximum.

Mean plasma concentration versus scheduled time profiles will be presented in figures on both linear and semilogarithmic scales. Individual plasma concentration versus nominal time profiles will be presented similarly.

9.4. Derivation of Pharmacokinetic Parameters

- The apparent C_{max} and the corresponding t_{max} along with T_{lag} will be read directly from the concentration-time plot (observed data).
- AUC_t will be calculated using the log-linear trapezoidal interpolation rule for extravascular model.
- The terminal elimination rate constant (λ_z) will be determined by log linear regression obtained on at least the 3 last quantifiable concentrations and will not include C_{max} ; $t_{1/2}$ is calculated by the program as $\ln 2/\lambda_z$;
- AUC_{∞} will be calculated by the program as: $AUC_{\infty} = AUC_t + AUC_{extrap}$ where last is the sampling time point of the last measurable concentration (t_{last}). AUC_{extrap} will be calculated by the program as: C_{last}/λ_z , where C_{last} is the observed concentration at time t_{last} and λ_z is the elimination rate constant during the apparent terminal elimination phase. AUC_{∞} will only be presented for participants with a reliable λ_z ;
- CL will be calculated by program as (molybdenum dose amount/ AUC_{∞});
- V_z will be calculated by the program as (molybdenum dose amount/ AUC_{∞})/ λ_z ;
- Dose normalized PK parameters will be calculated using the equivalent molybdenum dose and not the ALXN1840 dose. .

The following PK acceptance criteria will be applied to assess the reliability of elimination parameters:

- Number of points to calculate λ_z is greater than or equal to 3 excluding C_{max} point;
- The adjusted square of the correlation coefficient or coefficient of determination (Rsquare adjusted) for the goodness of fit of the regression line through the data points must be ≥ 0.90 ;
- $AUC_{extrap} \leq 20\%$.

Unreliable PK parameters will be listed but flagged and excluded from summary.

This document is confidential.

9.4.1. PK Parameters Summarization

Pharmacokinetic parameters derived from plasma concentrations of total and PUF molybdenum will be presented in data listings and summarized separately using the following descriptive statistics: number of participants, arithmetic mean, SD, arithmetic CV, geometric mean, geometric CV, median, minimum, and maximum.

9.5. Planned Statistical Models for PK Parameters and Concentrations

The primary analysis will be based on the PKDS-CO.

For the Period 1 and Period 2 comparisons, the PK parameters for total and PUF molybdenum (C_{max} , AUC_t , and AUC_{∞}) will be evaluated using an ANOVA statistical model with dosing period, treatment, and sequence as the fixed effects, and participant(sequence) as a random effect, using the natural logarithms of the data. Confidence intervals (CI, 90%) will be constructed for the least squares geometric mean ratio (GMR) for the 12 × 1.25 mg ALXN1840 mini-tablets versus a single 15 mg ALXN1840 tablet dose for all 3 PK parameters using the natural log-transformed data. The GMRs and the associated 90% confidence limits will be exponentiated back to the original scale.

The within-subject CV for the C_{max} , AUC_t , and AUC_{∞} will be estimated using the mean squared error from the ANOVA.

In addition, the geometric means and the associated 95% CIs of C_{max} , AUC_t , and AUC_{∞} will be reported for each treatment.

All secondary analyses will be based on the PKDS-E.

Dose-proportionality will be assessed across all EC mini-tablet treatments (2.5 mg, 5 mg, 10 mg, 15 mg, 30 mg ALXN1840) graphically and by using a power model (Smith, 2000; Newlands, 2006; EMA, 2010).

The following molybdenum dose-normalized PK parameters will be assessed for dose proportionality: C_{max_n} , AUC_{t_n} and AUC_{∞_n} . The log (PK parameters for plasma total and PUF molybdenum) will be included as a response variable and log (molybdenum dose) will be included as a fixed effect in the power model:

$$\log(\text{PK Parameter}) = \mu + \beta \cdot \log(\text{Molybdenum Dose})$$

*where $\beta = 1$ indicates perfect dose proportionality. Estimation of β , along with its 90% CI, will be provided.

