9.4.1.2. Analyses of Secondary Endpoints

All secondary analyses will be based on the PK Set.

Dose-proportionality will be assessed across all EC mini-tablet treatments (2.5 mg, 5 mg, 10 mg, 15 mg, 30 mg ALXN1840) graphically and by using a power model ([Smith, 2000](#); [Newlands, 2006](#); [EMA, 2010](#)). The following dose-normalized PK parameters will be assessed for dose proportionality: C_{max_n} , AUC_{t_n} and AUC_{∞_n} . The log (PK parameters for plasma total and PUF Mo) will be included as a response variable and log (dose) will be included as a fixed effect in the power model:

$$\log(\text{PK Parameter}) = \mu + \beta \cdot \log(\text{Dose})$$

where $\beta = 1$ indicates perfect dose proportionality. Estimation of β , along with its 90% CI, will be provided.

Additional approaches to test dose proportionality, such as an ANOVA model, will be explored ([Calvo, 2005](#)).

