5.2. Secondary PK Endpoints

Dose-normalized PK parameters for plasma total molybdenum and PUF molybdenum (C_{max_n} , AUC_{t_n} , and AUC_{∞_n})

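### The dose-proportionality section lists only dose-normalised parameters but gives a power-model slope of 1 as the ideal; for those parameters the ideal slope is 0

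*SAP*

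**What the plan says.** The secondary endpoint in SAP 5.2 is "Dose-normalized PK parameters for plasma total molybdenum and PUF molybdenum", that is, the normalised forms of Cmax, AUCt and AUCinf. SAP 9.5 carries this into the analysis: "The following molybdenum dose-normalized PK parameters will be assessed for dose proportionality", followed by the same three normalised parameters and no others. The next sentence reads "The log (PK parameters for plasma total and PUF molybdenum) will be included as a response variable", with log molybdenum dose as the fixed effect. It is followed by the equation log(PK parameter) = μ + β·log(molybdenum dose) and the statement that β = 1 "indicates perfect dose proportionality". The planned output is the estimate of β with its 90% CI. No acceptance range is given.

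Protocol 9.4.1.2 is built the same way: "The following dose-normalized PK parameters will be assessed for dose proportionality", then the power model and β = 1. The protocol adds "Additional approaches to test dose proportionality, such as an ANOVA model, will be explored"; the SAP does not take this up.

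SAP 9.4 fixes the divisor: "Dose normalized PK parameters will be calculated using the equivalent molybdenum dose and not the ALXN1840 dose". The quantity used to normalise is therefore also the regressor. SAP 9.6 and SAP 14 declare no departure from the protocol, so neither changes the reading.

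**The concern.** The parameters named for the assessment and the reference value given for the slope do not belong together. If the response is a parameter already divided by dose, proportionality appears as a flat line with slope 0. The stated ideal of 1 would then describe exposure growing with the square of the dose.

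The power model is the only model the SAP specifies for the secondary objective. With no acceptance limits, the reference value is the only standard the plan gives for reading the slope. A programmer who followed the text literally would report a slope near 0 for a well-behaved formulation next to an ideal of 1. If the mismatch is noticed only after the data are seen, someone has to choose the response or the reference at that stage, which a pre-specified plan should avoid.

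A smaller slip of the same kind is in SAP 10.1.2, where clearance normalised by molybdenum dose is plotted by BMI stratum. SAP 9.4 already computes clearance as molybdenum dose divided by AUCinf, and SAP 10.1.1 names plain clearance as the endpoint.

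**Working it through.** **Inputs.** Doses of 2.5, 5, 10, 15 and 30 mg (SAP 9.5); normalisation by molybdenum dose (SAP 9.4); stated ideal β = 1 (SAP 9.5); and, for a worked example, the Cmax that Protocol 4.3 anticipates: "for total Mo of approximately 40 ng/mL is anticipated after the lowest ALXN1840 dose of 2.5 mg".

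**Algebra.** Let P = c·D^β.

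- Un-normalised: log P = log c + β·log D. Proportionality (β = 1) gives slope 1, which reproduces the plan's figure.
- Normalised: log(P/D) = log c + (β − 1)·log D. Proportionality gives slope 0, so the plan's figure is not reproduced.

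**Worked example.** The left part of the table assumes exact proportionality from 40 ng/mL at 2.5 mg. The right part shows what a slope of 1 on the normalised scale would require.

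| Dose (mg) | Proportional Cmax (ng/mL) | Cmax/dose (ng/mL per mg) | Cmax/dose if its slope is 1 | Implied Cmax (ng/mL) |
|---|---|---|---|---|
| 2.5 | 40 | 16 | 16 | 40 |
| 5 | 80 | 16 | 32 | 160 |
| 10 | 160 | 16 | 64 | 640 |
| 15 | 240 | 16 | 96 | 1440 |
| 30 | 480 | 16 | 192 | 5760 |

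- Un-normalised slope: ln(480/40) / ln(30/2.5) = ln 12 / ln 12 = 1.00.
- Normalised slope: ln(16/16) / ln 12 = 0.00.
- For a normalised slope of 1, Cmax must rise by 5760/40 = 144 = 12² over the 12-fold dose range.

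All points lie exactly on a line, so a least-squares fit to the five doses gives the same slopes. True exponents of 0.8, 1.2 and 2.0 give normalised slopes of −0.2, 0.2 and 1.0.

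**Molybdenum dose or ALXN1840 dose.** If molybdenum dose is f·D with constant f, then log(f·D) = log f + log D. Only the intercept moves. Assumed fractions of 0.2 and 0.4 left every slope unchanged.

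**With variability.** A simulation under true proportionality used 10 participants in each extension dose group, 0 or 40 values at 15 mg, assumed CVs of 20%, 30% and 50%, independent observations and 4000 runs per setting. The 90% CI from normalised data covered 0 in 89% to 91% of runs and covered 1 in none. Un-normalised data gave the mirror image. The mean half-width was 0.05 to 0.14 and is identical for the two versions, because the slopes differ by a constant.

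**Clearance label.** (Molybdenum dose/AUCinf) / molybdenum dose = 1/AUCinf. At the single 15 mg crossover dose this only rescales the axis. It would vary with dose if the extension doses were pooled.

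**The case against.** The best defence is one of vocabulary. Elsewhere in both documents the unqualified phrase for PK parameters of total and PUF molybdenum is followed by un-normalised Cmax, AUCt and AUCinf, as in SAP 5.1 and in the primary analysis in SAP 9.5. Normalised values carry a qualifier or a suffix. On that usage the model response is un-normalised and β = 1 is correct. The list of normalised parameters could then belong to the graphical part of the assessment.

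This is a fair reading and may be what was intended. It does not rescue the text. The normalised list stands directly before the model, the secondary endpoint is defined only in normalised form, and nowhere are un-normalised parameters named for the power model. If un-normalised values were meant, the list and the declared endpoint do not match what is modelled. If normalised values were meant, the reference is wrong. A correction is needed either way.

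The points on limited harm stand. No decision rule uses β, the CI width does not change, and plots of normalised values would look flat for a proportional product, which should alert a careful reader. The 144-fold figure illustrates the algebra and is not a likely result. The clearance label may be loose wording for clearance computed from the molybdenum dose, and it is a minor point. Protocol 9.4 describes itself as a high-level summary, so the SAP edit is the one that matters most.

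**Conclusion.** The concern holds. For the parameters the plan lists, the stated ideal slope is too high by exactly 1.0. This is algebra and does not depend on sample size, variability or a constant molybdenum fraction; the CVs and the independence assumption enter only the illustrative simulation. What remains uncertain is which half of the text the authors meant, and the finding does not depend on that. The consequence is a wrong or unclear reference beside the secondary slope and its 90% CI. It can be corrected without new data. It should be fixed before analysis.

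**What to change.** In SAP 9.5, name un-normalised Cmax, AUCt and AUCinf as the power-model response, keep β = 1 as the reference, and reserve the normalised parameters for the graphs and any ANOVA. Alternatively, keep the normalised parameters as the response and state slope 0 as the reference. Make the matching change in Protocol 9.4.1.2 so that the documents agree. No acceptance range has to be added for this purpose.

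In SAP 10.1.2, drop the dose normalisation from the BMI plot and show CL/F, as the body-weight plot already does.

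The cost is one sentence in each document and one label in the SAP, with no new data and no effect on the primary analysis.
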